6.1.4 Arm A and Arm B: Cytarabine Consolidation

For patients age  $\geq 55$  or patients with decreased creatinine clearance recommend reducing consolidation cytarabine dose to 1.5 g/m^2.

Table 6-4 Guidelines for Cytarabine Dose Interruption or Discontinuation		
Dose Interruption or Discontinuation	Induction	Consolidation
Cerebellar Toxicity (any grade)	Discontinue	Discontinue
Direct Bilirubin $\geq 2$ mg/dL	NA	Interrupt*
Creatinine $>2$ mg/dL	NA	Interrupt*

\* Cytarabine may be interrupted for 72 hours. Gilteritinib/Midostaurin cannot be started until at least 48 hours after last dose of Cytarabine. If Cytarabine is not completed by Day 6, contact PrECOG to discuss schedule.

6.2 Concurrent Therapies

6.2.1 Permitted

Patients should receive full supportive care, including transfusions of blood and blood products, antibiotics, antiemetics, allopurinol, growth factors, etc., when appropriate.

**NOTE:** Prophylaxis with intrathecal chemotherapy is allowed prior to or during induction/consolidation.

6.2.2 Not Permitted

- Treatment with concomitant drugs that are strong inducers of CYP3A and P-gp are prohibited unless essential for the care of the patient.

6.2.3 Cautionary Use

Caution is advised when considering the following:

- Treatment with concomitant drugs that are strong inhibitors of P-gp and concomitant drugs that target serotonin 5HT2BR or sigma nonspecific receptor are to be avoided with the exception of drugs that are considered absolutely essential for the care of the subject.
- Treatment with concomitant drugs that are strong inhibitors of CYP3A should be avoided with the exception of antibiotics, antifungals and antivirals that are used as standard of care to prevent or treat infections. Grapefruit juice should not be ingested during study treatment. If strong CYP3A inhibitors are used concomitantly, patients should be closely monitored for AEs.
- Precaution should be used in use of gilteritinib with concomitant drugs that are known to prolong QT intervals or QTc. A cardiology consult should be obtained as medically indicated.
- Precaution should be used in use of gilteritinib with concomitant drugs that are substrates of P-gp, BCRP and OCT1, since these transporters have been shown to be inhibited by gilteritinib in in vitro studies.
- The investigator should consult individual labels for all drugs that the subject is taking to evaluate if they fall into any of the above named categories. (Appendix V: Additional Excluded and Cautionary Medications).

- Any other treatments of AML (including but not limited to chemotherapy, radiotherapy, surgery, HSCT, immunotherapy or cellular therapy) are prohibited during therapy.
  - Initiation of standard of care 7+3 induction chemotherapy using same regimen and dose as defined in protocol (Section 5.2.1) while awaiting prescreening test results is allowed.
  - Prophylaxis with intrathecal chemotherapy is allowed prior to or during induction/consolidation.
- Participation in another interventional study with an investigational agent while on treatment is prohibited.

## 7. Study Duration and Discontinuation of Therapy

### 7.1 Treatment Duration

Patients will receive protocol therapy as outlined unless:

1. Disease progression per Section 9 guidelines or clinical progression.
2. Toxicities considered unacceptable by either the patient or the investigator, despite optimal supportive care and dose modifications as per Section 6.
3. Patient proceeds to bone marrow transplant or any non-protocol leukemia directed therapy.
4. Development of an inter-current illness that prevents further administration of study treatment.
5. Extraordinary Medical Circumstances: If at any time the constraints of this protocol are detrimental to the patient's health, protocol treatment should be discontinued.
6. Patient withdraws consent or is unable to comply with study procedures.

### 7.2 Duration of Follow-Up

Patients will be followed for adverse events for 30 days after their last dose of study medication. However, if a patient experiences an adverse event >30 days after their last dose of study medication that is felt to be, in the opinion of the investigator, possibly, probably or definitely related to study therapy, the adverse event should be reported.

**NOTE:** Pregnancy within 180 days for WOCBP and for 120 days for a female partner of child-bearing potential after the final study drug administration will be reported and followed per Section 8.6.

Patients should be followed every 3 months from end of treatment for 2 years, then every 4 months for 1 year, then every 6 months for 1 year, then annually for progression and survival until death or study closure (+/- 1 month) whichever comes first. Patients should be seen up to the 2 year point at the treating institution. If the patient is unable to be seen at the treating institution, copies of office visit notes including labs with local oncologist should be obtained until year 5 per schedule above. Initiation of all anticancer therapy for current remission and first anticancer therapy for relapse will be documented.

If a patient is removed from treatment for reason(s) other than progression or full consent withdrawal, follow for survival/relapse until death or study closure.

For patients who are registered with tissue submitted for the study and are FLT3 negative or other condition, no further information will be collected after baseline demographics, sample submission, sample results and final diagnosis. For eligible patients randomized to the trial, but do not receive any protocol therapy, baseline, safety [as applicable] and end of treatment follow-up information per Section 10 will also be collected.

### 7.3 Criteria for Removal from Study Treatment

A genuine effort will be made to determine the reason(s) why a patient fails to return for the necessary visits or is discontinued from the trial, should this occur. It will be documented whether or not each patient completed the clinical study. If for any patient study treatment or observations were discontinued, the reason will be recorded on the appropriate electronic case report form. Reasons that a patient may discontinue treatment in a clinical study are considered to constitute one of the following:

1. If the patient has already initiated midostaurin or gilteritinib therapy and CNS involvement is detected, the patient may either come off protocol therapy immediately or complete therapy through Day 21 then will be removed from protocol treatment.
2. Failure to achieve CR or CRi after 2 cycles of induction.

3. Patient requires treatment with therapy not allowed per protocol, or patient goes on to receive HSCT.
4. Recurrence of disease or documented progression of disease.
5. Intercurrent illness that prevents further administration of treatment per investigator discretion.
6. Unacceptable adverse events.
7. Investigator and/or patient discontinue chemotherapy.
8. Pregnancy.
9. Develops a second malignancy (except for non-melanoma skin cancer or cervical carcinoma in-situ) that requires treatment, which would interfere with this study.
10. The patient may choose to withdraw from the study at any time for any reason.
11. General or specific changes in the patient's condition that render the patient unacceptable for further treatment in the judgment of the investigator.
12. Severe non-compliance to protocol as judged by the investigator.
13. Lost to follow-up.
14. Death.
15. Closure of study by PrECOG.

Patients who discontinue study treatment early should be followed for response assessments and survival, if possible. Follow-up will continue per Section 10, as applicable.

## 8 Adverse Event Reporting

### 8.1 Collection of Safety Information

**Adverse Event (AE)** is defined as any new untoward medical occurrence or worsening of a pre-existing medical condition in a patient administered a medicinal product in a clinical investigation and which does not necessarily have a causal relationship with this treatment. An AE can therefore be any unfavorable and unintended sign (e.g., including an abnormal laboratory finding), symptom, or disease temporally associated with the use of a product (investigational or marketed), whether or not considered related to the product (investigational or marketed).

After either informed consent, but prior to initiation of induction, only AEs/SAEs caused by a protocol-mandated intervention not considered standard of care will be collected (e.g., SAEs related to invasive procedures such as biopsies). Please note, if induction is started prior to randomization, AE/SAE collection will start at time of randomization. After the initiation of treatment on-study, any changes from baseline which meet (CTCAE V 5.0) Grade  $\geq 3$  AEs and SAEs must be recorded on the appropriate page of the electronic Case Report Form (eCRF). In addition, AEs less than Grade 3 that meet dose interruption, reduction or discontinuation criteria per Section 6.1 must also be recorded, including:  $\geq$  Grade 2 pancreatitis, QTc interval, PRES, cerebellar toxicity of any grade, creatinine  $>2$  mg/dL and direct or total bilirubin  $\geq 2$  mg/dL. All laboratory results required by protocol (Section 10) will be recorded directly on the laboratory eCRF pages. Per Sections 8.2 to 8.7 additional events will be recorded as AEs and/or SAEs (meeting definitions) on the appropriate eCRF.

If known, the diagnosis of the underlying illness or disorder should be recorded, rather than individual symptoms. The following information should be included for all documented AEs: date of onset and resolution, severity of the event; the investigator's opinion of the relationship to study drug (see definitions below); intervention or treatment required for the AE; action taken with study drug; cause of the event (if known); and information regarding resolution/outcome.

If the Grade  $\geq 3$  laboratory abnormality is a sign of a disease or syndrome (e.g., alkaline phosphatase and bilirubin 5x the ULN associated with cholecystitis), only the diagnosis (e.g., cholecystitis) needs to be recorded on the Adverse Event eCRF.

If the Grade  $\geq 3$  laboratory abnormality is not a sign of a disease or syndrome, the abnormality itself should be recorded as an AE or SAE on the eCRF. If the laboratory abnormality can be characterized by a precise clinical term in CTCAE Version 5.0, the clinical term should be recorded as the AE or SAE. For example, an elevated serum potassium level of 7.0 mEq/L should be recorded as "hyperkalemia".

Observations of the same Grade  $\geq 3$  laboratory abnormality from visit to visit should not be repeatedly recorded unless their severity, seriousness, or etiology changes.

#### Severity

The categories and definitions of severity used for clinical trials AEs are defined in the NCI's Common Terminology Criteria (CTCAE) V5.0 (<http://www.ctep.cancer.gov>).

#### Attribution

The following categories and definitions of causal relationship or attribution to study drug should be used to assess Adverse Events:

- **Definite:** There is a reasonable causal relationship between the study drug and the event. The event response to withdrawal of study drug (dechallenge) and recurs with rechallenge, if clinically feasible.

- Probable: There is a reasonable causal relationship between the study drug and the event. The event responds to dechallenge. Rechallenge is not required.
- Possible: There is a reasonable causal relationship between the study drug and the event. Dechallenge information is lacking or unclear.
- Unlikely: There is doubtful causal relationship between the study drug and the event.
- Unrelated: There is clearly not a causal relationship between the study drug and the event or there is a causal relationship between another drug, concurrent disease, or circumstances and the event.

Categories 'definite', 'probable' and 'possible' are considered study drug related. Categories 'unlikely' and 'unrelated' are considered not study drug-related.

The development of a new cancer should be regarded as an AE. New cancers are those that are not the primary reason for administration of study treatment and have been identified after inclusion of the patient into the clinical study.

**AEs related to cytarabine, daunorubicin, gilteritinib or midostaurin should be followed for 30 days after last dose of study therapy until  $\leq$  grade 1 or stabilization, and reported as SAEs if they become serious. Any AE's (serious or not) that occur more than 30 days after the last dose of study therapy but that are deemed to be at least possibly related to study therapy shall be reported.**

**NOTE:** Pregnancy within 180 days for WOCBP and for 120 days for a female partner of child-bearing potential after the final study drug administration will be reported and followed per Section 8.6.

## 8.2 Serious Adverse Events (SAEs)

A **serious AE** is any untoward medical occurrence occurring after initiation of study treatment or that at any dose:

- results in death (i.e., the adverse event actually causes or leads to death)
- is life-threatening (defined as an event in which the study patient was at risk of death at the time of the event; it does not refer to an event which hypothetically might have caused death if it were more severe)
- requires inpatient hospitalization or causes prolongation of existing hospitalization
- results in persistent or significant disability/incapacity
- is a congenital anomaly/birth defect
- is an important medical event (defined as a medical event(s) that may not be immediately life-threatening or result in death or hospitalization but, based upon appropriate medical and scientific judgment, may jeopardize the patient or may require intervention (e.g., medical, surgical) to prevent one of the other serious outcomes listed in the definition above).

Examples of such events include, but are not limited to, intensive treatment in an emergency room or at home for allergic bronchospasm; blood dyscrasias or convulsions that do not result in hospitalization.

## 8.3 Drug-Induced Liver Injury Adverse Events

The following adverse events must be reported to PrECOG as Serious Adverse Events, irrespective of regulatory seriousness criteria.

- Liver specific adverse events leading to study (study drug) discontinuation
- Hepatic laboratory abnormalities meeting potential Drug-induced Liver Injury criteria including:

- Any potential Hy's Law case\*, including those where review and adjudication concluded they did not meet the criteria
- All patients who died of hepatic illness
- All patients who discontinued trial drugs for hepatotoxicity, including patients with abnormalities consistent with protocol-specified stopping rules
- ALT and/or AST > 3x ULN AND Total Bilirubin > 2x ULN

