#### 6.1.2 Arm A: Gilteritinib

The dose levels include the following (Table 6-2):

Table 6-2 Gilteritinib Dose Levels	
Dose Level (DL)	Gilteritinib Dose
DL 1 (starting dose)	120 mg
DL -1	80 mg
DL -2	40 mg

The gilteritinib dose may be initially reduced by 1 dose level for a described instance meeting criteria for dose reduction. The study drug dose can be further reduced by a second dose level. Note that dose reductions should occur in a step-wise manner. Only 2 dose level reductions are permitted. Dose re-escalation is not allowed following dose reduction unless there is a specific reason not related to gilteritinib for temporarily holding or reducing gilteritinib.

Gilteritinib will be interrupted per Table 6-3. When the grade of the adverse event (AE) decreases to  $\leq 1$ , study drug may be resumed at the next lower dose level, unless the investigator deems the AE was, in retrospect, unlikely to be or not related to the study drug, at which point the original dose may be resumed.

Additionally, if the investigator deems it necessary to ensure subject safety, dosing may be interrupted or reduced for reasons other than those provided in Table 6-3. In the unusual circumstance that dosing is interrupted or reduced for reasons not specified in the table, the investigator should promptly inform PrECOG.

Missed doses of gilteritinib will not be made up.

Table 6-3 Guidelines for Gilteritinib Dose Interruption or Reduction Event	
Event	Action
First occurrence: Grade $\geq$ 3 nonhematological AE possibly, probably or definitely related to the study drug (excluding pancreatitis, see below)	Dosing will be interrupted. If the AE resolves to $\leq$ grade 1 within 14 days, the patient may resume dosing at the reduced dose during this or subsequent cycles. If the AE does not resolve to $\leq$ grade 1 within 14 days, the subject will be discontinued from treatment and an end of treatment visit will be performed.

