Second occurrence: Recurrence of the same nonhematological AE or appearance of other new nonhematological AE Grade $\geq$ 3 probably, possibly or definitely due to the study drug (excluding pancreatitis, see below)	Dosing will be interrupted. If the AE resolves to $\leq$ grade 1 within 14 days, the patient may resume dosing at the reduced dose during this or subsequent cycles. If the AE does not resolve to $\leq$ grade 1 within 14 days, the subject will be discontinued from treatment and an end of treatment visit will be performed.
Third occurrence: Recurrence of a prior nonhematological AE or appearance of other new nonhematological AE Grade $\geq$ 3 probably, possibly or definitely due to the study drug (excluding pancreatitis, see below)	The study drug will be discontinued.
At any point, in retrospect, if the investigator determines prior non-hematological Grade $\geq$ 3 AE which was initially attributed as possibly, probably or definitely related to study drug is now deemed unrelated	The study drug will be re-escalated to dose that the participant was on at the time of the AE.
Pancreatitis	Dosing will be interrupted until pancreatitis is resolved, then resume gilteritinib at 80 mg during this or subsequent cycles.
QTcF >500 ms	If the QTcF is >500 ms at any time point, the ECG will be repeated (within 2 hours or as soon as possible). Confirm that potassium and magnesium abnormalities are corrected. A cardiology consult will be obtained as medically indicated. If the repeat ECG confirms a QTcF >500 ms, dosing of study treatment will be interrupted. If QTcF resolves to $\leq$ 480 ms within 14 days from study drug interruption, subsequent dosing will be reduced to 80 mg (or if currently at 80 mg, reduction to 40 mg).
QTc interval increased by >30 msec over screening on ECG on Day 15 of Cycle 1	Confirm with ECG on Day 16. If confirmed, consider dose reduction to 80 mg. If currently at 80 mg, dose reduction to 40 mg.
Posterior Reversible Encephalopathy Syndrome (PRES)	Contact PrECOG, discontinue gilteritinib.

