### 6.1.3 Arm B: Midostaurin

Interrupt midostaurin for Grade 3/4 non-hematologic toxicity thought to be possibly related to midostaurin and restart at same dose when toxicity resolves to  $\leq$  Grade 1. If the toxicity resolves prior to day 21, then restart at same dose to complete current cycle. Missed doses will not be made up.

For QTcF >500, confirmed on repeat study, check potassium and magnesium and correct any abnormalities. If at that time QTcF is >480, restart at 50 mg daily, until QTcF is  $\leq$  480. Once QTcF  $\leq$  480 restart at 50 mg BID.

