### **7.5.6. Adverse Event**

An overall summary of adverse events by 2 treatment arms will be performed for induction and consolidation separately. It will include number and percentage of treatment-related AE (TrAE), Grade 3 or higher TrAE, serious TrAE, treatment-related grade 3 or higher AE leading to stop treatment and study discontinuation, death, etc. The worst grade of treatment-related non-hematological AE for each patient will also be summarized by treatment arms for induction and consolidation separately.

The following AEs are considered as hematological AEs:

Anemia, CD4 lymphocytes decreased, Lymphocyte count decreased, Neutrophil count decreased, Platelet count decreased, and White blood cell decreased.

All others that are not in the above list will be classified as Non-hematological AEs.

All collected adverse events are coded in MedDRA version 23.0. The treatment-emergent adverse events (TEAE) are defined as database collected AE that onset on or after the first protocol treatment (Gilteritinib or Midostaurin) date or worsening of a pre-existing AE after treatment. TrAE is defined as the investigators' assessed drug-related adverse events and their causality after drug is administered. All TrAE will be summarized by system organ class and preferred term and 2 treatment arms and displayed in frequency order.

All TrAEs that onset before the first dose of consolidation treatment will be summarized in induction tables. The TrAEs that onset on or after the first dose of consolidation treatment will be summarized in consolidation tables.

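### The liver-discontinuation SAE trigger in Protocol 8.3, combined with a mandatory stop that only Arm A has, may bias the serious-TrAE percentage against gilteritinib for a narrow class of events

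*Protocol*

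**What the plan says.** Protocol 8.3 opens with: "The following adverse events must be reported to PrECOG as Serious Adverse Events, irrespective of regulatory seriousness criteria". Two of the triggers listed there depend on a decision to stop drug: "Liver specific adverse events leading to study (study drug) discontinuation" and "All patients who discontinued trial drugs for hepatotoxicity, including patients with abnormalities consistent with protocol-specified stopping rules". The others do not: a potential Hy's Law case, death from hepatic illness, and the laboratory criterion "ALT and/or AST > 3x ULN AND Total Bilirubin > 2x ULN". No arm is named.

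The rules on stopping the FLT3 inhibitor are in Section 6.1 and differ by arm.

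- **Arm A (6.1.2, Table 6-3).** For a related Grade 3 or higher non-hematological event, first or second occurrence, that has not come down to Grade 1 within 14 days: "the subject will be discontinued from treatment and an end of treatment visit will be performed". At a third occurrence: "The study drug will be discontinued".
- **Arm B (6.1.3).** For Grade 3/4 non-hematologic toxicity possibly related to midostaurin, the drug is interrupted, with the instruction to "restart at same dose when toxicity resolves to" Grade 1 or lower. There is no time limit, no count of occurrences and no instruction to discontinue.

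SAP 7.5.6 gives numbers and percentages by arm, for induction and consolidation separately. They include "serious TrAE, treatment-related grade 3 or higher AE leading to stop treatment and study discontinuation". No test is specified, and SAEs that meet the 8.2 criteria are not separated from those that are SAEs only through 8.3.

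**The concern.** A count of serious events supports a comparison between arms only if the same event is classified the same way in both. Here SAE status can follow from discontinuation, and discontinuation follows from arm-specific rules. Part of any difference in the serious-TrAE row could then reflect the reporting rule and not the drugs.

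Toxicity in each arm is a secondary objective (Protocol 2.2), and percentages shown side by side will be read as a comparison even without a test. Raised liver transaminase is an identified risk of gilteritinib (Protocol 11.1.9.3), so an artefact would fall where readers expect a real signal.

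**Working it through.** The plan states no figure for this, so the check is a comparison of rules followed by an illustration of size.

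**1. One event, two classifications.** Take a related Grade 3 transaminase rise that meets no 8.2 criterion and no other 8.3 trigger, and resolves on its 15th day after interruption.

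| | Arm A | Arm B |
|---|---|---|
| Section 6.1 rule | Not resolved within 14 days: discontinue | Interrupt; restart permitted on resolution |
| 8.3 stopping trigger | Met | Not met, unless someone decides to stop |
| Serious TrAE row | Counted | Not counted |
| Grade 3 or higher TrAE row | Counted | Counted |

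The forced stop in Table 6-3 applies only to events judged possibly, probably or definitely related. Every SAE it creates is therefore a *related* SAE and enters the serious-TrAE row.

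**2. Other routes to a stop.** These apply to both arms:

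- unacceptable toxicity, by judgement (Protocol 7.1, 7.3; repeated for midostaurin in 5.2.4);
- the requirement that significant toxicity has settled before consolidation (5.2.2).

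An Arm B patient stopped for hepatotoxicity by either route is also an SAE under 8.3. The cytarabine liver rule (Table 6-4) is an interruption, the same in both arms. Within Section 6.1, then, the only mandatory study-drug stop that reaches liver events is in Arm A.

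**3. Which events are affected.** Only related Grade 3 or higher liver events that persist beyond 14 days or are a third occurrence, that meet neither 8.2 nor an arm-neutral 8.3 trigger, and that occur in patients with no other serious TrAE in the same table.

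**4. Size.** All three rates below are assumptions.

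- b = share of patients with a serious TrAE for other reasons: 10%, 20%, 30%.
- q = share of Arm A patients whose only route to SAE status is a stop for a liver event: 1%, 2%, 5%.
- r = rate of such stops in Arm B relative to Arm A: 0, 0.5, 1.
- n = 85 per arm, half of the 170 eligible patients in Protocol 12.1, taken as an approximation to the safety population.

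Excess in Arm A = (1 − b) × q × (1 − r).

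Example: b = 0.10, q = 0.05, r = 0 gives 0.90 × 0.05 = 4.5 points, or 85 × 0.045 = 3.8 patients.

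| r = 0 | q = 1% | q = 2% | q = 5% |
|---|---|---|---|
| b = 10% | 0.9 points (0.8 patients) | 1.8 (1.5) | 4.5 (3.8) |
| b = 20% | 0.8 (0.7) | 1.6 (1.4) | 4.0 (3.4) |
| b = 30% | 0.7 (0.6) | 1.4 (1.2) | 3.5 (3.0) |

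At r = 0.5 each entry halves; at r = 1 it is zero.

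For scale, the half-width of a 90% confidence interval for the arm difference is 1.645 × √[pA(1 − pA)/85 + pB(1 − pB)/85], with pA = b + (1 − b)q and pB = b + (1 − b)qr. Over these scenarios it runs from 7.7 to 11.9 points. The artefact is smaller than the sampling uncertainty in every case shown.

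**The case against.** Most of the opposing case has weight.

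- *8.3 treats the arms alike, and Arm B can stop too.* Both are true. The asymmetry arises only when 8.3 is combined with 6.1, and Arm B's routes rest on judgement or on the pre-consolidation condition; neither forces a stop at 14 days. A reader might infer that Arm B can contribute no such SAEs. The documents do not support that. Nor do they say whether midostaurin that never meets its restart condition counts as discontinued.
- *Other outputs would expose the artefact.* SAP 7.5.6 also reports Grade 3 or higher TrAEs, worst grade of non-hematological TrAEs, and all TrAEs by preferred term. SAP 7.5.7 adds laboratory shifts and maximum grades. Similar grades beside unequal serious counts would be a warning. A reader might infer that the artefact could not be told from a real liver signal; these tables show otherwise. They do not correct the serious-TrAE row itself.
- *The liver signal is weak at the trial dose.* Protocol 1.3.4 reports hepatic enzyme elevation as dose limiting only above 300 mg/day; this trial starts at 120 mg. For gilteritinib with chemotherapy in new AML, the same section lists no hepatic term among Grade 3 or higher events in at least 10% of patients, and none among serious drug-related events in more than one subject. A reader might assume that as many as 10% of patients have an affected event, and test that against none in Arm B. Neither the rate nor the zero is supported, and the SAP plans no such test.
- *The direction could reverse.* Arm A resumes at a reduced dose and Arm B at the same dose with no occurrence limit, which could add genuine SAEs in Arm B. That would be a treatment effect and would not remove the classification difference, but it does leave the net direction open.
- *The protocol's own toxicity summary is maximum grade per type (12.2.2), not SAEs.* True, and it limits the importance of the point.

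**Conclusion.** The point holds in a limited form. For related, persistent or third-occurrence Grade 3 or higher liver events that are not otherwise SAEs, classification can depend on the arm, and SAP 7.5.6 does nothing to separate them. The serious-TrAE percentage *may* be biased against gilteritinib. The stronger statement that it *is* so biased does not follow, because the number of affected events, the frequency of Arm B stops and the net direction are all unknown.

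The size is probably small. The 0.7 to 4.5 points rest on assumed b and q and on no such stops in Arm B; the excess disappears if stops are equally frequent. The table is descriptive. The templates that accompany the SAP are a separate document and were not available, so they may already contain a relevant split. This is a cheap improvement to a safety table, not a threat to the trial's conclusions.

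**What to change.** In SAP 7.5.6:

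1. Keep the full serious-TrAE row, so that it still agrees with the SAE reports.
2. Flag events reported as SAEs only because of a discontinuation trigger in 8.3, and show serious TrAEs by arm with and without them.
3. Add a row by arm for the 8.3 laboratory criterion, derived from the collected values. AST, ALT and total bilirubin follow one schedule for both arms (Protocol 10) and are recorded on the laboratory eCRF pages (8.1). State how transaminase and bilirubin values are paired in time.
4. State the differing arm rules wherever the serious-TrAE and AE-related discontinuation rows are interpreted.

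The cost is one flag and two rows. Two cautions apply. The documents do not say whether the SAE form records which seriousness criterion was met, so this must be confirmed. And the important-medical-event criterion in 8.2 rests on judgement in an open-label trial: an event that forced a stop could be coded there, so the split may not remove all of the difference. The laboratory row is not exposed to that judgement. Nothing here changes a reporting duty or a dosing or stopping rule.
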